the project: *  If 'No' was answered to the previous question, explain how the confidentiality of patheir data will be protected, and include whether the research procedures or collect may reasonably be expected to identify an individual:  All participants will be given an identifier on their data collection sheets, and information will be collected.  Identify any factors that may limit the researchers' ability to guarantee confidential Limits due to the nature of group activities, such as a focus group where the	rticipants and ted information no identifying ity:
the project: *  If 'No' was answered to the previous question, explain how the confidentiality of patheir data will be protected, and include whether the research procedures or collect may reasonably be expected to identify an individual:  All participants will be given an identifier on their data collection sheets, and information will be collected.  Identify any factors that may limit the researchers' ability to guarantee confidential.  Limits due to the nature of group activities, such as a focus group where the project team cannot guarantee confidentiality:  Limits due to context: individual participants could be identified because of the	rticipants and ted information no identifying ity:
If 'No' was answered to the previous question, explain how the confidentiality of patheir data will be protected, and include whether the research procedures or collect may reasonably be expected to identify an individual:  All participants will be given an identifier on their data collection sheets, and information will be collected.  Identify any factors that may limit the researchers' ability to guarantee confidential Limits due to the nature of group activities, such as a focus group where the project team cannot guarantee confidentiality:  Limits due to context: individual participants could be identified because of the nature or size of the sample:  Limits due to context: individual participants could be identified because of their	rticipants and ted information no identifying ity:

# **Risks and Benefits**

Explain the psychological, emotional, physical, social or legal harms that participants may experience during or after their participation: The study has three minor ethical issues. First is the perceived risk of zoonotic disease transmission in the ED.

Second is the potential negative patient reaction to a therapy dog presence in the ED.

Third, there may be some minimal discomfort experienced by patients in taking their anxiety biomarkers.

Describe how the above risks will be managed. If appropriate, identify any resources to which they can be referred:

First, during the pilot study the team applied the American Veterinary Medical Association therapy dog visiting guidelines and we developed RUH ED specific visiting protocols. These will apply to the proposed study. We also have the expertise of [name] ([name]) on our research advisory group.

Second, Policies and procedures have been developed to ensure the health and safety of patients, staff, therapy dogs and handlers (e.g., approaching patients upon consent, signage in the ED). Our team also conducted a patient study in the ED waiting room in 2017 and found that more than 80% of participants agreed or strongly agreed that people would want to visit a therapy dog.

Third, the discomfort experienced by patients in taking their anxiety biomarkers is minimal and not out of the ordinary of regular ED procedures.

IT IS IMPORTANT TO NOTE that the therapy dogs regularly visit the RUHD ED, and have been doing so for three years, irrespective of this study.

Describe the likely benefits of the research that may justify the above risk(s): The clinical relevance and benefits of this study to RUH pain patients is grounded in recognition of the potential benefits of animals in human pain patient health care in the ED. Examining the impact of a unique psychosocial health intervention on pain patients' experiences in a hospital ED can offer a complementary understanding of quality health care. There have been no studies of therapy dogs in EDs in Canada, one opinion survey in the US has been undertaken, and a recent (2019) controlled trial in a US ED department with therapy dogs. The US opinion study found that "93% of patients and 95% of staff agreed that therapy dogs should visit EDs". This finding highlights what is widely accepted in the companion animal literature but infrequently by ED medicine and medicine generally; interacting with animals can benefit human bio-psycho-social-spiritual health. The controlled study found that "Exposure to therapy dogs plus handlers significantly reduced anxiety in ED patients".

# **Part 3: Community Engagement**

# **Aboriginal Peoples and Community Engagement**

Aboriginal communities, peoples, language, culture or history is the primary focus of this project: *	☐ Yes ⊠ No
Aboriginal people will comprise a sizable proportion of the larger community that is the subject of research even if no Aboriginal-specific conclusions will be made: *	☐ Yes ☐ No ☐ Not Applicable

There is an intention to draw Aboriginal-specific conclusions from this project: *	☐ Yes ⊠ No
This project will involve community-based participatory research: *	☐ Yes ⊠ No
There will be a research agreement between the researcher and community:	☐ Yes ⊠ No

# **Aboriginal Engagement and Community-Based Participatory Research**

If 'yes' was answered to any of the above questions, complete the following:

Outline the process to be followed for consulting with the appropriate community:

Describe the organizational structure and community processes required to obtain approval within the specific community(ies):

Describe any customs and codes of research practice that apply to the particular community(ies) affected by the project:

Describe how the research plan will consider mutual benefit to the participating community(ies), support capacity building through enhancement of the skills of community personnel and the recognition of the role of elders and other knowledge holders:

Describe how the community representatives will have the opportunity to participate in the interpretation of the data and the review of research findings before the completion of any reports or publications:

Describe how the final project results will be shared with the participating community(ies):

#### **PART 4: RECRUITMENT AND CONSENT**

# **Participant Recruitment**

Indicate the expected number of participants and provide a brief rationale for the number:

A sample size of at least 122 in both the control and animal intervention is required to detect statistically significant results based on information collected on patient response in the pilot study.

Describe the criteria for including participants:

Participants will be over the age of 18, able to provide consent, attending the ED because of pain and want to visit with a therapy dog. These patients are located in the 'active area' of the ED in individual curtained-off spaces with beds; the patients are either waiting to be seen by a physician, have treatment in progress, or are admitted to hospital and waiting for a unit bed. Participants will also be willing to visit with a therapy dog team (although the control group will not be visiting with a dog).

Describe the criteria for excluding participants:

The RA will access the patient's Medication Administration Record (MAR) to confirm non-administration of pain medications (specifically immediate release acetaminophen and opioid analgesics) within the hour prior to the visit. This step is included to prevent confounding the potential effect of the therapy dog intervention on pain outcomes.

Provide a detailed description of the method of recruitment, such as how and whom will identify and contact prospective participants:

RA #1 will identify patients who are verbally coherent and interested in visiting with a therapy dog. Consent will be obtained from pain patients to participate in the study. All ED patients can visit with a therapy dog, regardless of study participation. The RA will access the patient's Medication Administration Record (MAR) to confirm non-administration of pain medications (specifically immediate release acetaminophen and opioid analgesics) within the hour prior to the visit. This step is included to prevent confounding the potential effect of the therapy dog intervention on pain

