## **Part 2: PROJECT OVERVIEW**

# **Project Overview**

Summarize this project, its objectives and potential significance:

The goal of this unique 18 month study is to better understand the experiences of pain patients in the Royal University Hospital (RUH) Emergency Department (ED) to create excellence in health care. The purpose is to measure the impact of visiting therapy dogs on reducing ED patient pain. The background rationale is that pain is the primary reason individuals attend an ED, patient pain is generally not well managed in EDs, Saskatchewan EDs have among the longest wait times in the country, and anxiety associated with ED waiting can negatively impact patients' pain. Research suggests a therapy dog can change patients' perceptions of pain and its intensity and facilitate relaxation. The intervention will be examined for its impact on patients' sensory pain (i.e., physical pain severity), affective pain (i.e., emotional pain unpleasantness) and anxiety. It is important to find creative, low-cost ways to respond to patients attending the ED for pain. The primary objective of this study is to generate new health-related knowledge on the ED pain patient experience. The secondary objectives are to implement effective end-of-grant knowledge translation and dissemination strategies and undertake a successful model of collaborative, multidisciplinary research among researchers, patient advisors and system representatives, rooted in a One Health framework.

Provide a description of the research design and methods to be used:

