St. John Ambulance Therapy Dog teams are comprised of a certified (tested and passed) therapy dog and handler. The goal of the St. Johns Ambulance therapy dog program is to offer support and comfort to individuals the dogs visit with. Five therapy dog teams commonly visit the RUH ED five days a week. The visits follow a standardized protocol (i.e., sign in, patients interact with the therapy dog, handlers share information about the dog). In this study therapy dogs will visit a convenience sample of consenting RUH ED pain patients five days a week. Each therapy dog team will participate once-a-week, for a 90 minute period, and during peak and low patient ED wait times (by day of the week and time). Participants will be over the age of 18, able to provide consent, attending the ED because of pain and want to visit with a therapy dog. These patients are located in the 'active area' of the ED in individual curtained-off spaces with beds; the patients are either waiting to be seen by a physician, have treatment in progress, or are admitted to hospital and waiting for a unit bed. A

control group will also be involved, with the same process and sample.

Data will be collected 3 days/ week (alternating with control days). Data will be collected in five steps, using quantitative psychometric measures that will not exceed 10 minutes. Patient pain will be measured with the Edmonton Symptom Assessment System (revised version) (ESAS-R) (numerical pain scale) and patient anxiety will be measured with biomarkers (heart rate, blood pressure) and the ESAS-R (anxiety, depression and overall wellbeing questions). The Human-Animal Interaction Scale (HAIS) will be applied to document the behaviour and amount of interaction between the therapy dog and patient. Quantitative data analysis using both descriptive and inferential statistical procedures will be conducted to examine distributions, relationships and differences among variables. Measures of outcome variables will be compared between pre- and post-therapy dog intervention and the influence of moderator variables, such as gender, will be examined. The HAIS score will indicate the quantity of positive human-animal interaction.

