**Data collection tools** 

- -ESAS-R (indicate on picture; scale 1-10)
- -Main reason for attending the ED
- -Heart rate and blood pressure
- -ESAS-R numerical scale (anxiety, depression, wellbeing)
- -Patient demographics
- -HAIS form

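### The one-hour analgesic exclusion is checked only against the Medication Administration Record, so some self-taken or pre-arrival doses within the hour may be missed

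*Protocol*

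**What the plan says.** The exclusion criterion in Protocol Part 4, Participant Recruitment, has the research assistant "access the patient's Medication Administration Record (MAR) to confirm non-administration of pain medications". The drugs and window are "specifically immediate release acetaminophen and opioid analgesics) within the hour prior to the visit". The reason follows: "This step is included to prevent confounding the potential effect of the therapy dog intervention on pain outcomes". The same instruction is repeated in the recruitment paragraph of that section. The Medication Administration Record (MAR) is the only source named in either place.

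Eligible patients are in active-area beds, and "the patients are either waiting to be seen by a physician, have treatment in progress"; a third group is already admitted but not yet moved to a ward. The Project Overview (Part 2) describes the same population and adds that a "control group will also be involved, with the same process and sample".

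Under Duration and Location of Data Collection Events, the questions put to the patient before the visit are described as covering pain, anxiety and demographics. The list of data collection tools at the end of the application has six entries: two for the ESAS-R, then "Main reason for attending the ED", heart rate and blood pressure, demographics and the HAIS form. None refers to medication.

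**The concern.** The protocol treats a recent analgesic dose as a confounder whatever its origin, but looks for it only in a record of drugs administered. For a patient not yet seen by a physician, an empty MAR says little about what was taken at home, from the patient's own supply in the ED, or received before arrival. As written, an empty MAR passes the check.

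At stake is the change in pain between the two scores. A dose taken shortly before the first score may still be taking effect at the second, and the resulting fall would be counted as part of the response to the visit. Later analysis cannot adjust for a dose that was never recorded, so this cannot simply be left to the analysis plan.

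**Working it through.** **1. The source against its purpose.** The purpose is to prevent confounding by analgesia in the hour before the visit. The source is the MAR alone. No patient question or pre-arrival record is named in Participant Recruitment, in the questionnaire description or in the tool list. The gap is therefore any dose within the hour that staff did not enter.

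**2. Who can fall into the gap.** The window is one hour before the visit, not before arrival. A pre-arrival dose counts only if arrival, bed placement, identification and consent all follow within 60 minutes of it. For patients in treatment or admitted, such a dose will usually lie outside the window, and even a complete record would not exclude them. The Project Overview says that "Saskatchewan EDs have among the longest wait times in the country", which narrows the pre-arrival route further. It does not close the other route, self-dosing while waiting in the ED. The group concerned is thus mainly patients seen soon after arrival and patients dosing themselves on site.

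**3. Which comparison is affected.** The Project Overview plans a pre/post comparison around the dog visit, and there is also a control group. Let f be the share of patients with a missed dose and m the extra fall in pain it causes between scores, in SDs of the change.
- Dog-arm pre/post change: shift = f × m, whatever happens in the control group.
- Dog-control difference: bias = (f on dog days − f on control days) × m. This is zero if the shares are equal; missed doses then only add variance.

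**4. Scale (illustrative).** The plan gives at least 122 per group, but no alpha, power, effect size or SD, so that figure cannot be reproduced. I assume two-sided 5%, 80% power and m = 0.5 to 1.0 SD. The documents give neither f nor m.
- Detectable difference: (1.960 + 0.842) × sqrt(2/122) = 0.359 SD.
- SE of the dog-arm change: 1/sqrt(122) = 0.091 SD.
- SE of the dog-control difference: sqrt(2/122) = 0.128 SD.
- Power with equal shares uses SD = sqrt(1 + f(1 − f)m²).

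| Missed share f | Dog-arm pre/post shift (SD) | Same, in SEs | Power, equal shares |
|---|---|---|---|
| 2% | 0.01-0.02 | 0.11-0.22 | 79.8-79.2% |
| 5% | 0.025-0.05 | 0.28-0.55 | 79.5-78.2% |
| 10% | 0.05-0.10 | 0.55-1.10 | 79.1-76.5% |
| 20% | 0.10-0.20 | 1.10-2.21 | 78.4-73.9% |

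For unequal shares with no true effect, type I error = 1 − Φ(1.96 − b/0.128) + Φ(−1.96 − b/0.128), where b is the bias:
- 5-point imbalance: b = 0.025-0.05 SD, type I error 5.4-6.8%.
- 10-point imbalance: b = 0.05-0.10 SD, type I error 6.8-12.2%.

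**The case against.** The best case for the plan has four parts.

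- **The window is short and recruits are already in beds.** This stands and limits the point. A reader might infer that recently dosed patients in general pass as unmedicated. The one-hour rule and the long waits do not support that; only a subset can.
- **Both groups follow the same process, so missed doses cancel.** This stands for the dog-control contrast when the shares are equal. It does not protect the pre/post change in the dog arm. Nor does it guarantee equal shares, since groups are formed by day from a convenience sample.
- **The documents do not say what this ED enters in its MAR, and the data forms are not shown.** This also stands. A reader might infer that the MAR cannot show home or ambulance doses, or that no form asks about medication. The documents establish only that the MAR is the sole named source and that no medication item is mentioned. That such a record would not normally show self-taken doses is a general expectation.
- **The protocol makes no false statement.** True: it speaks of non-administration and does not claim to detect self-medication. But it gives the step the task of preventing confounding, and the named source covers only part of that task.

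**Conclusion.** The point holds as a gap in an eligibility check, not as a demonstrated bias. Some patients with a dose within the hour may pass. How many cannot be judged from the document.

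The consequence is clearest for the dog-arm pre/post change, which missed doses would inflate to the extent that the drug is still taking effect between the scores. For the dog-control contrast they add noise, and they bias it only if their share differs between dog and control days. Allocation by day does not prevent such a difference, but nothing in the documents shows its size or direction.

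A reader might infer from the upper rows of the working that a dog effect could easily be manufactured by unseen dosing. The documents do not support this. A missed share of 10-20% or a 10-point imbalance is pure assumption, and the one-hour window makes the larger shares hard to reach. At 5% missed equally in both groups, the cost is under 2 percentage points of power and no between-group bias. The case for acting is that the remedy is cheap and that the plan as written could not reveal the problem if it occurred.

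**What to change.** In Part 4, Participant Recruitment, keep the MAR check and add one question, put to the patient before baseline and worded identically on dog and control days: any acetaminophen or opioid from any source, and when. Apply the protocol's existing one-hour rule to the answer as well as to the MAR. Add a line to the data sheet for time since last dose, so that a sensitivity analysis is possible. A look at any ambulance record in the chart is optional; it adds a data source that the application does not describe, and the fix does not depend on it.

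The cost is under a minute per patient, reliance on the patient's recall, and a few more patients excluded or deferred. No extra staff are needed.

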Control group data will be collected 2 days/ week (alternating with animal testing days) with a goal of 8 samples per day. The data collection will occur in two stages. First, patient pain will be measured with the Edmonton Symptom Assessment System (revised version) (ESAS-R) (numerical pain scale) and patient anxiety will be measured with biomarkers (heart rate, blood pressure) and the ESAS-R (anxiety, depression and overall wellbeing questions). The HAIS scale will not be administered during the control as there will be no animal interaction. Control days require two research assistants who will obtain consent using a deceptive consent form which will explain that this is a pain study but will omit any information regarding therapy dogs. Once all measures are taken the participants will be explained the deception and asked to sign the true consent form.

All of our team members will meet on a monthly basis. The team represents a solid compliment of expertise, experience and knowledge (contributing from data collection through to end-of-grant knowledge translation). This will enable the team to fully deliver on the project goal, purpose and objectives. The outcomes of this study will be meaningfully translated and disseminated to improve the health care of RUH ED pain patients with peer reviewed publishing, RUH monitor adverts and webinar, and a news release. The clinical relevance of this study is that the outcomes will offer a complementary understanding of quality health care for ED pain patients. To date there have been no studies of therapy dogs in EDs in Canada.

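### Research assistants who know whether it is a dog day or a control day choose a convenience sample, so the patients approached can differ between groups before baseline is measured

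*Protocol*

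**What the plan says.** - **Allocation (Protocol, Project Overview).** Group follows the calendar. For the dog group: "Data will be collected 3 days/ week (alternating with control days". For controls: "Control group data will be collected 2 days/ week (alternating with animal testing days) with a goal of 8 samples per day". No randomisation or concealment of the day is described.
- **Who knows the group (Project Overview; Consent Process).** "Control days require two research assistants who will obtain consent using a deceptive consent form". The Consent Process section explains that the deception keeps control patients unaware of the dogs and of being controls. It does nothing to mask staff.
- **Who is chosen (Project Overview; Participant Recruitment).** The sample is described as a "convenience sample of consenting RUH ED pain patients". The method of recruitment is that "RA #1 will identify patients who are verbally coherent and interested in visiting with a therapy dog".
- **When baseline is taken (Duration and Location of Data Collection Events, Questionnaires).** The candidate is identified first. The pain, anxiety and demographic questions follow.
- **What limits the choice (Participant Recruitment).** Patients must be adults able to consent, in the ED for pain, and in a bed in the active area. The medication record must show no immediate-release acetaminophen or opioid in the preceding hour. Interest in a dog is required of both groups: "Participants will also be willing to visit with a therapy dog team (although the control group will not be visiting with a dog".
- **Comparability (Project Overview).** Controls are said to follow the same process and to be the same kind of sample. No procedure is given for achieving this.

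**The concern.** With allocation by day, the group is settled before any patient is seen. What then protects the comparison is that patients are taken up in the same way on both kinds of day. Here a recruiter who knows the group uses judgement over whom to approach, and does so before the first measurement. Even without intent, the patients who seem easy to approach for a dog visit may differ from those who seem easy to approach for a pain questionnaire.

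The main comparison is at stake. A difference in pain or anxiety after the visit could partly reflect who was picked. A larger sample does not help, because the bias stays while the standard error shrinks. Nor can the analysis recover it in full, since the way patients are approached is settled on the ward and leaves no trace unless it is recorded at the time.

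**Working it through.** No arithmetic yields the size of this problem. The one related figure, 122 per group, cannot be reproduced from the protocol, which gives no significance level, power, effect or standard deviation. The point does not depend on it. The check is whether each link in the chain is in the text.

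1. **Is the group known before approach?** Yes. It is fixed by the day, and staff on control days carry a different consent form.
2. **Is there discretion over whom to approach?** Yes. The stated rule is convenience sampling by RA #1, with no consecutive, random or bed-order sequence.
3. **Does selection come before measurement?** Yes. Baseline questions follow identification of the candidate.
4. **Are the two day types run alike?** Not as written:
   - *Session length:* a dog team takes part for 90 minutes. No session length is given for control days.
   - *Target:* control days have "with a goal of 8 samples per day". No daily target is given for dog days.
   - *Dog interest:* required of both groups. On dog days it can be asked openly. On control days the consent form omits dogs until all measures are complete, so it cannot be asked openly beforehand.
5. **Does anything stated close the gap?** Only in part. The eligibility criteria and medication check define who may enter, but not which of the eligible patients are approached. The statement that controls follow the same process is an aim without a mechanism.

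**Is there room to give up some recruiting freedom?** The study runs from 1 June to 30 November 2019, which is 183 days, or about 26 weeks. If data collection stopped at the end of October because the ED moves in November, it would be 153 days, or about 22 weeks.

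| | 26 weeks | 22 weeks |
|---|---|---|
| Control days at 2 a week | 52 | 44 |
| Controls needed per day | 122/52 = 2.3 | 122/44 = 2.8 |
| Dog days at 3 a week | 78 | 66 |
| Dog patients needed per day | 122/78 = 1.6 | 122/66 = 1.8 |

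At the stated goal, controls accrue at 2 × 8 = 16 a week, and 122/16 = 7.6 weeks would be enough. On these figures a somewhat slower approach rule is affordable.

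**The case against.** The strongest reply has four parts.

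- **Silence is not absence.** This is an ethics application with short answers, and the data forms are only listed. A reader might infer that no record of patients passed over is kept. The text supports only that none is described. That stands. The point therefore rests on the convenience rule, which is a stated choice.
- **The pressures on staff are conjecture.** A reader might infer that staff seek out patients suited to an animal on dog days and take anyone available on control days to reach 8. Neither is in the text. The recruitment wording refers to the patient's interest and asks the same of controls. Eight is a goal, and the accrual figures above show little need to strain for it. That stands as well.
- **The criteria are not as loose as they look.** The medication-record check is objective and bears directly on pain. It narrows discretion, but it does not say which eligible patient is approached.
- **Baseline is measured.** Pain and anxiety scores are taken before the visit, so adjustment can largely remove a difference in baseline pain, and the analysis plan is not at hand to show that it would be omitted. This is right for what is measured. It does not reach approachability, alertness or affinity for dogs, which may bear on later scores at a given baseline.

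**Conclusion.** The point holds as a possibility that the design leaves open: the patients approached can differ by group. The protocol does not show that they will. The conclusion rests on the stated allocation by day, staff knowledge of the day, discretionary convenience sampling and selection before baseline. It needs no assumed figure.

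A reader might go further and attach an inflated false-positive rate. Suppose the outcome SD is 2 points, selection shifts mean baseline pain by 0.5 points, and 30% to 50% of that carries into the change score. The bias is then 0.5 × 0.3 = 0.15 to 0.5 × 0.5 = 0.25 points. The standard error is 2 × √(2/122) = 0.256, and a two-sided 5% test rejects about 9% to 16% of the time with no true effect. The arithmetic is correct, but the documents do not support using it as the size of this problem:

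- The SD, the shift and the carry-over are all assumed. None is in the protocol.
- The bias runs only through baseline pain, which is measured and can be adjusted for.
- The direction is open. If calmer patients with lower pain were picked on dog days, regression to the mean would make the dog group improve less, and false findings in its favour would fall below 2.5%, to about 0.5% (bias 0.15) or 0.2% (bias 0.25).

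Neither size nor direction can be derived from the protocol. The change is still worth making before data collection, because it is cheap and the information cannot be recovered afterwards.

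**What to change.** 1. **Approach order.** Replace the convenience rule with one rule for both day types: a start bed set in advance for each date, then every pain patient in the active area in bed order until the session closes.
2. **Session window.** State one window of the same length for dog days and control days.
3. **Tally.** Keep an anonymous count of patients approached, ineligible (with reason) and declined, and report it by day type. It needs no identifying data, so it fits the protocol's anonymity commitment.
4. **Dog-interest screen.** Specify one screen, in the same words and at the same point, that works on both day types. One possibility is an item within a short list of comfort services, subject to the ethics board's view on whether it preserves the concealment. Without this, the eligible groups and the refusal counts would not be comparable even with a fixed approach order.

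The cost is a one-page tally and a pre-printed start bed for each session, with no extra staff foreseen. The downside is possibly slightly slower accrual. These steps do not deal with differences between the days themselves. Randomly assigning days would address those, but it would not stop selection by staff who know the day.
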